Electrical stimulation to evoke recto-colonic reflex for colonic motility

Funding Agency: VA RR&D

Principal Investigator: [name], DO

1593201-8/12-3-21/2021

Abstract

This study hopes to characterize the effects of minimally invasive electrical rectal stimulation on colonic motility in persons with neurogenic bowel dysfunction. Subjects will act as their own controls, with control data being obtained during subjects' typical bowel routines. Outcome measures include bowel emptying duration and amount of stool removed. These data will be compared to determine the efficacy of electrical stimulation to promote bowel emptying compared to patients' typical bowel routines, and to provide an effect size on the outcome measures of colonic motility for powering future studies.

We hypothesize that electrical rectal stimulation will produce increased colonic motility that results in defecation and that defecation time will be similar to subjects' typical bowel routines. The time required for defecation in response to their typical bowel routine and to minimally invasive electrical rectal stimulation will be monitored. Subjects will also be asked to report on sensations and comment on electrical stimulation.

List of Abbreviations

LSCDVAMC: Louis Stokes Cleveland DVA Medical Center

SVAMC: Syracuse VA Medical Center

SCI: spinal cord injury

EMG: electromyogram

AD: autonomic dysreflexia

NBD: neurogenic bowel dysfunction

FES: functional electrical stimulation

IRB: Institutional Review Board

Contents

1.0	Study Personnel	5
2.0	Introduction	5
3.0	Objectives	6
4.0	Resources and Personnel	6
5.0	Study Procedures	7
5.1	Study Design.....	7
5.2	Recruitment Methods	8
5.3	Informed Consent Procedures	9
5.4	Inclusion/Exclusion Criteria	9
5.5	Study Evaluations	10
5.6	Data Analysis.....	10
5.7	Withdrawal of Subjects	11
6.0	Reporting.....	11
7.0	Privacy and Confidentiality.....	11
8.0	References	12

Protocol Title: Electrical stimulation to evoke recto-colonic reflex for colonic motility

2.0 Introduction

Loss of bowel function is a major concern for veterans with central nervous disorders, such as spinal cord injury (SCI). Over 42,000 veterans have SCI, representing more than 15% of the total American population with SCI. Following SCI, the colon is often unable to evacuate stools via peristaltic propulsion. Losing bowel function can cause constipation, gastro-intestinal complications, and fecal incontinence, severely impacting health and quality of life.

The standard of care for individuals with neurogenic bowel dysfunction involves the design of a bowel program for predictable and effective elimination of the bowels. A bowel program includes diet, fluid intake, activity, and pharmaceutical or mechanical rectal stimulation. Approximately 80% of individuals with neurogenic bowel dysfunction use digital stimulation of the rectum to reflexively activate the colon, improve colonic motility, and facilitate bowel evacuation. However, the bowel routine can require over an hour to evacuate the bowels and this process often requires the assistance of a caregiver, which adds to the cost of care and reduces independence. Restoring bowel function is considered a high priority by individuals with paraplegia, but it remains a critically unmet need requiring further development. The top priority for individuals with tetraplegia is reaching and hand function, but pelvic functions are still of high concern.

Digital rectal distension is the clinical standard for eliciting colon motility. The majority of individuals with neurogenic bowel dysfunction use digital rectal stimulation to mechanically distend the rectum and reflexively activate colon peristalsis, which loads stool into the rectum for bowel emptying. Digital rectal distension takes advantage of an existing reflex pathway affecting bowel function. The recto-colonic reflex has been well-studied in cats, dogs, and humans. Rectal distension activates mechanoreceptors innervating the rectum, which sends afferent information via small A δ and C fibers to the sacral spinal cord. This input modulates a spinal reflex pathway that activates motor efferent drive to the colon, causing coordinated peristalsis and increasing colonic motility. Digital rectal stimulation is effective, but it requires an individual, or a caregiver, to reach into the individual's rectum with gloved fingers. Even with digital

rectal stimulation and other bowel program tools, the bowel routine still typically requires an hour or two to complete. Reliance on digital rectal stimulation is associated with lost independence, lost time, lost dignity, and increased caregiver costs. Substituting rectal distension for a method that does not include these drawbacks would provide positive social and psychological benefits.

We are currently developing approaches using electrical stimulation to improve colonic motility as an alternative to digital rectal stimulation and to take advantage of the rectocolic reflex. Recent preclinical experiments have provided supporting evidence that electrical stimulation of the rectum or distal colon can modulate this excitatory rectocolic reflex and potentially promote bowel emptying. We hope to quantify the effects of minimally invasive electrical rectal stimulation, in comparison to subjects' typical bowel emptying routine, on colonic activity in persons with neurogenic bowel dysfunction.

3.0 Objectives

This pilot study hopes to characterize the effects of minimally invasive electrical rectal stimulation on colonic motility in persons with neurogenic bowel dysfunction, as well as collect data to determine an effect size and so power future studies that measure colonic motility in response to electrical stimulation

Our hypothesis is that electrical rectal stimulation will produce increased colonic motility that results in defecation and that defecation time will be similar to subjects' typical bowel routines.

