
Typical bowel routines usually involve digital rectal stimulation conducted by the subject, their nurse, or their caregiver. An individual inserts a gloved finger through the anus into the rectum and mechanically distends the rectum by moving back and forth against the inside of the rectal wall for approximately 30 seconds. Time is allowed for the colon to move and evacuate some stools, then the process is repeated (typically 15-20 minutes later). Digital rectal stimulation is thus repeated until the colon contents are empty, usually marked by the appearance of mucus and no evidence of stools in the distal colon or rectum. Some subjects may also receive a mini-enema or other

suppository to aid in bowel emptying. Individual bowel routine schedules vary but are typically conducted 3-5 times a week.

Electrical Rectal Stimulation

A clinically standard rectal probe electrode will be inserted into the rectum to administer electrical stimulation. The probe electrode will only be in place to administer bouts of stimulation just as gloved fingers administer digital rectal distension, after which it will be removed to allow for bowel emptying. The probe electrode will be connected to a Digitimer stimulator DS7A, which is FDA-approved for electrical stimulation in human subjects and has been used in our previous, similar experiments for bladder function. Stimulation will either be 20 Hz constant frequency or burst pattern stimulation delivered as 5-50 pulses at 100-200 Hz once per second. We will first determine the stimulation amplitudes at which the subject can sense stimulation and at what limit they tolerate stimulation but do not wish to go higher for concern of discomfort. We will then apply stimulation within this range, not expected to exceed 40 mA, which is the typical range we see in similar applications of surface electrical stimulation. Stimulation will be administered continuously for the duration of the bowel routine. If stimulation does not increase colonic motility and promote defecation, as determined by each subject's baseline data on bowel emptying time, nurse experience, or clinician expertise, then we will cease stimulation for that day and return to the subject's typical bowel routine. If stimulation fails to increase colonic motility for bowel emptying on 3 or more occasions in a given subject, then we will stop the 6-week stimulation period and return that subject to their typical bowel routine.

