5.6 Data Analysis

This work is considered a pilot study. Data will be collected to determine an effect size and power future studies that measure colonic motility in response to electrical stimulation. Therefore, 10 subjects are chosen to provide sufficient data to power a future study.

Bowel emptying will be performed by a trained clinician, caregiver, or subject (whoever normally performs it for the subject) using standard technique. The bowel routine is typically conducted with digital rectal stimulation and/or the insertion of suppositories or similar chemical systems. The time that elapses between initial intervention and bowel emptying will be measured as bowel emptying time. We will also test electrical stimulation to modulate an excitatory recto-colic reflex by stimulating via a rectal probe electrode. These systems are clinically available for chronic constipation in other indications and are considered minimal risk. We have experience measuring bowel activity with these methods. Initial introduction of the rectal probe electrode may cause temporary distension of the rectum. To ensure that reflexive activity due to the probe does not confound our data, we will wait approximately 5-10 minutes for the colon to relax back to baseline activity before beginning the bowel routine with stimulation.

The primary outcome variable is bowel emptying time. Bowel emptying time data are not expected to follow a normal distribution. Therefore, the non-parametric Mann-Whitney rank-sum test with a significance of 0.05 will be used to compare bowel emptying times between typical bowel routines and electrical stimulation conditions

across subjects. We expect to observe a great deal of variability in bowel emptying times, which may require many observations and subjects to achieve statistical significance.

Analysis on de-identified data will be performed by study staff. De-Identified data from this study may be pooled with data collected by [name] originating from a similar study of the same name currently approved at the Louis Stokes Cleveland DVA Medical Center.

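### Whether stimulation produces defecation is half of the hypothesis, but no outcome measures it, and the plan does not say how failed stimulation sessions enter the emptying-time comparison

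*Combined protocol and SAP*

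**What the plan says.** The hypothesis in section 3.0, repeated in the abstract, has two parts. The first is that "electrical rectal stimulation will produce increased colonic motility that results in defecation"; the second is that the time to defecation resembles that of the typical routine.

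Section 5.6 addresses the second part only. It states that "The primary outcome variable is bowel emptying time", defines it ("The time that elapses between initial intervention and bowel emptying will be measured as bowel emptying time"), and names one test: the "non-parametric Mann-Whitney rank-sum test with a significance of 0.05 will be used to compare bowel emptying times". Section 5.5 refers back to 5.6 for outcome measures. The abstract is slightly wider ("Outcome measures include bowel emptying duration and amount of stool removed"), but 5.6 gives stool amount no analysis.

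Section 5.1, under Electrical Rectal Stimulation, sets a rule for sessions that do not work: "If stimulation does not increase colonic motility and promote defecation, as determined by each subject's baseline data on bowel emptying time" or by nursing or clinical judgement, "then we will cease stimulation for that day and return to the subject's typical bowel routine". Failure on three or more occasions ends that subject's stimulation period. Nothing in the document makes this judgement an outcome, says it will be summarised, or says what emptying time a failed session receives.

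**The concern.** Electrical stimulation is meant to take the place of digital stimulation, so the first question is how often it works and the second is how long it takes when it does. The plan answers only the second, and does so with a quantity whose meaning depends on how failures are handled.

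Section 5.1 allows failure to be judged against the subject's own baseline emptying time, so slow sessions are the likely failures. A report of similar times could then sit on top of a sizeable, unreported failure rate. The pilot exists to size later studies, and a later replacement study cannot be planned well without knowing how often the method works.

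**Working it through.** The plan's only design figure, 10 subjects, comes with no effect size, SD, margin or power, so it cannot be reproduced. The checks below do not depend on it except in step 4. Failure rates, time distributions and intraclass correlations (ICC) are assumptions, because the documents give none.

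**1. Failed sessions dropped.** Let times be log-normal and identical in both conditions, with failure meaning no emptying before the control q-quantile. The retained times have their median at the q/2 quantile, so the ratio to the control median is exp(σ·z), where σ = √ln(1+CV²) and z is the normal quantile at q/2. For CV 0.3, 0.5 and 0.8, σ = 0.294, 0.472 and 0.703.

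| Cut | Sessions failing | z | Ratio at CV 0.3 / 0.5 / 0.8 |
|---|---|---|---|
| 75th percentile | 1 in 4 | −0.3186 | 0.911 / 0.860 / 0.799 |
| 90th percentile | 1 in 10 | −0.1257 | 0.964 / 0.942 / 0.915 |

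The median looks 9–20% or 4–9% shorter with no true difference.

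**2. Failed sessions kept.** Give each failed session the cut time plus one fresh control time, as if the typical routine then ran its course. Every failed session still lies above the control median, so the median ratio is 1.00 in all six cases. The mean is 1–19% longer by simulation. The apparent shortening disappears, but the recorded times now combine two methods, and the median does not reveal that 1 session in 4 or 1 in 10 failed.

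**3. The three-failure stop.** Sessions per sequential subject: every other day for 6 weeks gives 42/2 = 21; the 3–5 per week also stated in 5.1 gives 18–30. Stopping is modelled at exactly the third failure, with a constant failure rate f.

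- The chance of reaching three failures in 21 sessions, 1 − P(Binomial(21, f) ≤ 2), is 0.085, 0.352, 0.821 and 0.973 at f = 5%, 10%, 20% and 30%. Over 18–30 sessions it is 0.27–0.59 at 10% and 0.73–0.96 at 20%.
- Expected stimulation sessions fall from 21 to 13.8 at f = 20% and 9.9 at 30%.
- The expected raw success fraction per subject is Σ(k=0..2) P(k failures in 21)·(21−k)/21 + Σ(m=3..21) C(m−1,2)·f³·(1−f)^(m−3)·(m−3)/m. This gives 0.879, 0.743 and 0.625 when the truth is 0.90, 0.80 and 0.70.
- Replacing the fraction by 1 − 2/(n−1) for subjects stopped at session n returns 0.90, 0.80 and 0.70.
- That correction needs a constant rate. With assumed failure of 40% in sessions 1–5 and 10% in sessions 6–21, true average success is 1 − (5×0.40 + 16×0.10)/21 = 82.9%. The corrected estimate averages about 68%, and pooled successes over attempts about 78%.
- Pooling is unbiased if all subjects share one rate, but not otherwise: with half the subjects at 95% and half at 50%, the mean rate is 72.5% and pooling gives 84.8%.

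**4. Attainable precision.** Half-width = 1.96·√[p(1−p)·(1+20·ICC)/210], for 10 × 21 = 210 sessions with no early stops. At p = 0.70 it is about 6, 11, 16 and 21 percentage points at ICC 0, 0.1, 0.3 and 0.5.

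**The case against.** The strongest reply is that a failed session may still yield an emptying time. The subject goes back to the typical routine the same day, and time is counted from the initial intervention to emptying. A reader might infer that emptying time exists only for sessions that empty under stimulation, and hence that the planned comparison is biased towards shorter times. The documents do not support either inference: they do not say whether such times are excluded, censored or kept, and step 2 shows the shortening vanishes under one plausible handling. What stands is that the rule is missing.

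A reader might also infer that a success record already exists for each session. Section 5.1 requires a judgement and, in effect, a count of failures. It does not say that the judgement is stored as data, and it allows more than one basis for it. A definition and a field are therefore needed.

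A third tempting step is to prescribe the inverse-sampling correction. Several stimulation patterns and a range of amplitudes are allowed, so early sessions may fail more often, and step 3 shows the correction can then be far off. It belongs in a sensitivity analysis.

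It can fairly be added that stool amount bears on whether defecation occurs. It does, but 5.6 does not analyse it and it is not a success rate. Subjects within 6 months of injury alternate methods and have no separate stimulation period, so the 21-session frame does not describe them, although the same record does. Finally, a stimulation-only rate is not a comparison with digital stimulation, and with 10 subjects it will be imprecise. Both are reasons to report it modestly, and neither is a reason to omit it.

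**Conclusion.** The point holds in this form: the first half of the hypothesis has no outcome or analysis, the judgements that bear on it are required by the protocol but unused, and the treatment of failed sessions in the primary comparison is undefined. This should be changed.

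The 4–20% shortening is illustrative. It applies only if failures are dropped, and rests on log-normal times, CVs of 0.3–0.8 and the two percentile cuts. The downward bias in the mean of raw subject fractions (about 74% when the truth is 80%) rests on 21 sessions, a constant rate and a stop at exactly the third failure. The gap in the plan depends on none of these assumptions.

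**What to change.** In section 5.6:

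- Name session success as an outcome beside emptying time, with one fixed definition for analysis: emptying reached under electrical stimulation with no return to the typical routine that day. Record it for every attempted stimulation session, in both sequential and alternating subjects.
- Report successes over attempted sessions for each subject, the number of subjects stopped under the three-failure rule, and a subject-level summary with a 95% CI. Note that the mean of raw subject fractions is pulled down by the stop. Give an inverse-sampling estimate only as a sensitivity analysis, stating that it assumes a constant failure rate.
- State that a failed session is never analysed as a stimulation emptying time without being identified as a failure, and that emptying time is interpreted only together with the success rate.

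The cost is a paragraph, one recorded field per session and one more estimate, which may be less favourable than the time result. No visits are added and the clinical stopping rule is untouched.

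### The hypothesis is similarity and the aim is an effect size, but section 5.6 plans only an unpaired difference test, with no margin, estimator or confidence interval

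*Combined protocol and SAP*

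**What the plan says.** - **Hypothesis (Abstract and 3.0).** Stimulation will produce defecation, and "defecation time will be similar to subjects' typical bowel routines". Neither place says how close counts as similar.
- **Aim (Abstract, 3.0 and 5.6).** The Abstract wants "to provide an effect size on the outcome measures of colonic motility for powering future studies". Section 5.6 says "Data will be collected to determine an effect size and power future studies" and justifies the sample size with "10 subjects are chosen to provide sufficient data to power a future study".
- **Design (Abstract).** "Subjects will act as their own controls". Section 5.1 gives each subject more than six months after injury a 6-week control period and then a 6-week stimulation period, with a routine typically every other day. Subjects nearer to injury alternate between the two conditions.
- **Analysis (5.6).** The "Mann-Whitney rank-sum test with a significance of 0.05 will be used to compare bowel emptying times" between conditions, across subjects. No margin, effect measure, estimator, confidence interval, paired method or unit of analysis is given.
- **Stopped sessions (5.1).** When stimulation does not work, "then we will cease stimulation for that day and return to the subject's typical bowel routine". The stimulation period ends early "If stimulation fails to increase colonic motility for bowel emptying on 3 or more occasions in a given subject". Section 5.6 defines emptying time as running from the first intervention until the bowel is emptied. It does not say how that applies to a stopped session.

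**The concern.** The planned output does not answer the stated questions, for four reasons.

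1. A test for a difference can count against similarity, but failing to reject does not support it. Nothing in the plan guards against reading it that way.
2. The pilot's main product is an effect size, and none is defined. The measure, and the treatment of stopped sessions, would be chosen after the data are seen.
3. Mann-Whitney assumes two independent samples. Here the same subjects supply both conditions, many times each, so the p-value is not valid.
4. Stopped sessions are selected for poor response. Leaving them out would pull the estimate towards the hypothesised similarity.

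**Working it through.** **The plan's own figure.** The plan gives no SD, effect size, power, margin or precision target. Ten subjects therefore can be neither reproduced nor called wrong.

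**Inputs.** From the documents: 10 subjects, alpha 0.05, and every other day for 6 weeks, which is 42/2 = 21 sessions per condition. Assumed, on the log scale: between-subject SD 0.1-0.5, SD of subjects' response to stimulation 0.2, session SD 0.4. Log time is modelled as subject effect + session error, plus (log ratio + response effect) under stimulation. A 25% lengthening is log 1.25 = 0.223.

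**Reading 1: one value per subject (10 v 10).** The SD of a subject's log ratio of means is √(0.2² + 2 × 0.4²/21) = 0.235. For the paired t-test the noncentrality is 0.223/(0.235/√10) = 3.0. Mann-Whitney leaves the between-subject spread in the noise. By simulation:

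| Analysis | Misses a true ratio of 1.25 |
|---|---|
| Mann-Whitney, between-subject SD 0.1 / 0.2 / 0.3 / 0.4 / 0.5 | 36 / 62 / 84 / 94 / 98% |
| Paired t on mean logs | about 24% |
| Signed-rank on subject medians | about 30-33% |

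When times are truly equal, Mann-Whitney rejects in about 0-3% of trials instead of 5%.

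**Reading 2: all routines pooled (210 v 210).** The error runs the other way. With the same SDs, the test rejects in about 11-27% of trials when times are truly equal, and misses a ratio of 1.25 in only about 3-10%. The excess comes from subjects differing in their response. If they did not differ, a separate simulation on standardised data with 18-30 routines per period gives about 1-3% false rejection.

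**Precision of the effect size.** With 10 pairs, an observed standardised paired effect of 0.5 has a noncentral-t 95% CI of -0.17 to 1.15. An SD estimated from 10 subjects has a 95% CI of 0.69 to 1.83 times the estimate.

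**Stopped sessions.** Assume, for illustration only, that a session is stopped at 1.5, 2 or 2.5 times the subject's control median and that the period ends at the third failure (between-subject SD 0.4).

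- *Dropped:* a true ratio of 1.25 is estimated as about 1.01, 1.15 and 1.21.
- *Ranked longest:* the stimulation median is not reached in 37.0, 9.8 and 2.2% of subjects. At n = 10 the signed-rank 95% limits are the 9th smallest and 9th largest of 55 Walsh averages. One unreached subject makes 10 of these infinite, so one is enough to remove the upper limit. The chance of at least one, 1 - (1 - q)^10, is 99, 64 and 20%; simulation gives about 99, 63 and 21%.

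**The case against.** This is a pilot. It need not be powered for equivalence, and 5.6 itself warns that variability may make significance hard to reach. A difference test also suits the Abstract's separate aim of comparing efficacy with the usual routine. Both points stand. They do not supply the missing effect measure, and they do not make an unpaired test right for paired data.

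The 36-98% figure rests on one reading. That is correct: 5.6 does not state the unit, and its remark about needing many observations fits pooling at least as well. Pooling does not rescue the test, because it exchanges missed differences for false ones.

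The 5.6 definition can also be read to give a stopped session an observable time that includes the resumed routine. This too stands. It argues for keeping that time, and against making a longest rank the primary rule. The stopping thresholds above are invented: 5.1 also allows nurse experience or clinician expertise to decide.

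A reader might infer that the investigators intend to declare similarity from a non-significant result, or to size the next study on the observed effect alone. The documents say neither. The fault is that they leave both open.

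**Conclusion.** The mismatch is established from the text alone: a similarity hypothesis, an effect-size aim and a within-subject design are served only by an unpaired difference test, and its p-value is not valid for these data. The fault should be fixed.

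The sizes are illustrations that depend on the assumed SDs. Direction depends on the unit: with one value per subject the test is too insensitive, and with pooled routines it rejects too often if subjects differ in response. The bias from dropping stopped sessions is always towards similarity under the assumed stopping model, but its amount depends on thresholds that the plan does not give. The alternating schedule for subjects within six months of injury was not modelled. None of this shows that 10 subjects is the wrong number for a pilot.

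**What to change.** **In 5.6, replace the Mann-Whitney test with:** *The primary result is the within-subject ratio of bowel emptying times (stimulation/control), from one median per subject and condition, with a Hodges-Lehmann estimate and 95% CI and the matching Wilcoxon signed-rank test. Between- and within-subject SDs are reported. A non-significant p-value is not evidence of similarity.*

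**Add, for sessions in which stimulation is stopped:** *They are kept, not dropped, using the full time from first intervention to bowel emptying, including the resumed routine. Their number and proportion are reported by subject.* Ranking them longest may be a sensitivity analysis only, with disclosure of how often its upper limit may be unbounded.

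**Replace the sentence justifying 10 subjects with:** *The pilot gives an effect estimate and SDs with their uncertainty.*

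**In 3.0,** either reword similarity as a descriptive estimation aim, or fix a margin before data are seen and conclude similarity only if the 90% CI lies within it.

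**Cost.** Wording only; no extra subjects or visits. There are two real downsides.

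- Similarity may have to be reported as not established. With an illustrative margin of 0.80-1.25 (not a proposal), truly equal times, no stopped sessions and paired logs, the 90% CI lies inside in about 74, 32 and 10% of trials at response SDs of 0.2, 0.3 and 0.4. The descriptive wording avoids this.
- The full time of a stopped session mixes stimulation with the usual routine, so the ratio must be read beside the stopped-session rate.
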